eMC Electronic Medicines Compendium

ESC European Society of Cardiology

EudraCT European Clinical Trials Database

FSH Follicle Stimulating Hormone

GCP Good Clinical Practice

GDPR General Data Protection Regulations

GP General Practitioner

HRA Health Research Authority

HSCIC Health and Social Care Information Centre

HTA Health Technology Assessment

ICF Informed Consent Form

ICH International Conference on Harmonization

IDMC Independent Data Monitoring Committee

IMP Investigational Medicinal Product

ISF Investigator Site File

ISR Investigator safety report

ISRCTN International Standard Randomised Controlled Trial Number

ISTH International Society for Thrombosis and Haemostasis

ITT Intention to Treat

IUD Intrauterine Device

IUS Intrauterine Hormone-Releasing System

LAM lactational amenorrhoea method

LT Life-Threatening

MACE Major Adverse Cardiovascular Events

MALE Major Adverse Limb Events

MHRA Medicine and Healthcare products Regulatory Agency

MI Multiple Imputation

MRC Medical Research Council

NCA National Competent Authority

NCI National Cancer Institute

NHS National Health Service

NICE National Institute for Health and Clinical Excellence

NIHR National Institute of Health Research

PAD Peripheral arterial disease

PI Principal Investigator

PID Participant Identification number

PIS Participant Information Sheet

PPI Patient and Public Involvement

PROMs Patient-reported Outcome Measures

QALY Quality-adjusted Life Year

QAP Qualitative Analysis Plan

QL (QoL) Quality of Life

R&D Research and Development

RCT Randomised Controlled Trial

REC Research Ethics Committee

RSI Reference Safety Information

SAE Serious Adverse Event

SAP Statistical Analysis Plan

SAR Serious Adverse Reaction

SCARs Severe Cutaneous Adverse Reaction

SmPC Summary Product Characteristics

SOP Standard Operating Procedure

SUSAR Suspected Unexpected Serious Adverse Reactions

SWAT Study Within a Trial

TIA Transient Ischemic Attack

TIMI Thrombolysis In Myocardial Infarction

TM Trial Manager

TMF Trial Master File

TMG Trial Management Group
TSC Trial Steering Committee

UKCRC United Kingdom Clinical Research Collaboration

USM Urgent Safety Measure
UTI Urinary Tract Infection

1 Amendment History

The following amendments and/or administrative changes have been made to this protocol since the implementation of the first approved version.

Amendment No.	Protocol version no.	Date issued	Summary of changes made since previous version
N/A	1.0		First version

2 Synopsis

Short title	Clopidogrel, Aspirin and Rivaroxaban after revascularisation with angioplasty for limb-threatening Peripheral Arterial Disease		
Acronym	CLARITY PAD		
Internal ref. no.	UID 948		
Clinical phase	Phase IV		
Funder and ref.	NIHR HTA 154252		
Trial design	Pragmatic, adaptive multicentre open-label three-arm individually randomised controlled trial (RCT)		
Trial participants	Adults undergoing percutaneous or hybrid endovascular intervention for Chronic Limb Threatening Ischemia (CLTI)		
Planned sample size	1,239		
Planned number of sites	Around 20		
Inclusion criteria	 Adults (aged 18 years and over) undergoing percutaneous or hybrid endovascular intervention for CLTI of the lower limbs Atherosclerosis as the cause of CLTI Target arteries: infrainguinal (common femoral to pedal) if percutaneous, or iliac to pedal if performed as part of hybrid revascularisation with common femoral endarterectomy Clinicians would use trial antithrombotic combinations in normal clinical practice Able to provide informed consent First time in the CLARITY trial 		
Exclusion criteria	 Open bypass as part of hybrid procedure Intervention for asymptomatic restenosis of a bypass graft Pre-existing indication for dual antiplatelet therapy or anticoagulant e.g. atrial fibrillation Active malignancy or any other non-vascular condition associated with a life expectancy of less than 36 months Embolic arterial disease Renal failure with creatinine clearance <15ml/minute Thrombophilia or any other inherited or acquired bleeding disorder Persons of childbearing potential who have a positive pregnancy test, are breastfeeding or attempting pregnancy 		
Treatment duration	12-36 months		
Follow-up duration	Up to 36 months		
Planned trial period	01 January 2024 – 01 January 2029		
Primary objective	To compare the clinical effectiveness of three commonly used antithrombotic regimens (clopidogrel; aspirin plus clopidogrel; aspirin plus low-dose rivaroxaban) following endovascular intervention for CLTI		
Secondary objectives	 To evaluate the clinical and cost-effectiveness of clopidogrel; aspirin plus clopidogrel; aspirin plus low-dose rivaroxaban following endovascular intervention To evaluate the delivery of the CLARITY trial and trial interventions 		

Tertiary/Exploratory objectives	To explore how the trial interventions work in the real healthcare system
Primary outcomes	Primary effectiveness outcome: A composite event-free survival time of:
Secondary outcomes	 Major adverse limb events (MALE) (defined as amputation or major reintervention of the trial limb) Major adverse cardiovascular events (MACE) (defined as recurrent CLTI, amputation affecting contralateral limb, acute coronary syndrome, ischaemic stroke) Bleeding Academic Research Consortium (BARC 2, 3 or 5) and Thrombolysis In Myocardial Infarction (TIMI) defined major bleeding Minor bleeding Primary and secondary patency of artery Reintervention Healing of tissue loss Health-related quality of life (VascuQoL-6 and EQ-5D-5L) Cost-effectiveness Qualitative process evaluation
Tertiary/Exploratory outcomes	 MALE using other major definitions (composite outcome using trial variables) MACE using other major definitions (composite outcome using trial variables) Complications from trial medications Qualitative exploration of trial intervention implementation, feasibility and acceptability
Investigational medicinal products	ClopidogrelAspirin plus ClopidogrelAspirin plus Rivaroxaban
Form	Tablet
Dose	Clopidogrel 75mg (once/day) Aspirin 75mg (once/day) plus clopidogrel 75mg (once/day) Aspirin 75mg (once/day) plus rivaroxaban 2.5mg (twice/day)
Route	Oral

[figure not shown]

3. Trial summary & schema

3.1 Trial schema and Participant flow

Exclusion criteria (~60%): Open bypass as part of hybrid procedure; Pre-existing indication for dual antiplatelet therapy or anticoagulant e.g. atrial fibrillation; Active malignancy or any other non-vascular condition associated with a life expectancy of less than 36 months; Reintervention for asymptomatic bypass graft stenosis; Embolic arterial disease; Non-atherosclerotic peripheral arterial disease (PAD); Renal failure with creatinine clearance <15ml/minute; Thrombophilia; Inherited and acquired bleeding disorders; Persons of childbearing potential who have a positive pregnancy test, are breastfeeding or attempting pregnancy; Inability to provide

Figure 1. Trial Schema and participant flow

3.2 Trial lay summary

THE PROBLEM:

Blocked leg arteries are very common and are often caused by diabetes or smoking. Blocked leg arteries are becoming more common as diabetes becomes more common and can lead to amputation, or even death if left untreated. Each year in the UK, between 16,500 and 30,000 people die and 3500 legs are amputated because of heavily blocked leg arteries. The most common way to reduce these risks is to open the blocked arteries with a balloon or stent, a procedure called an angioplasty.

Over 4000 angioplasties to increase blood flow in the leg are performed each year in the UK. Patients are given blood-thinning tablets after this treatment to reduce the risk of artery-blocking again and reduce the risk of amputation. These tablets also reduce the risk of other arteries in the body blocking, preventing heart attack, stroke or death. There are several different tablets and combinations available.

RESEARCH IMPORTANCE:

Sometimes two blood thinners are given together. If two blood thinners work better than one, we may be able to save up to 1600 lives and prevent 800 amputations each year in the UK by using them routinely. The problem with two blood thinners is that they cause more life-threatening bleeding than one. This might be up to 700 more bleeds per year in people having an angioplasty.

AIMS:

Our trial will compare three different combinations of tablets for thinning the blood after angioplasty:

- 1) Clopidogrel,
- 2) Aspirin and Clopidogrel,
- 3) Aspirin and Rivaroxaban.

The aim is to see which tablet(s) are best at preventing complications of blocked arteries after angioplasty and to make sure any combination does not cause too much bleeding.

WHAT WE HAVE ALREADY DONE:

No-one knows which blood-thinning tablet or tablets, are best. When we surveyed vascular surgeons in the UK, they mainly used the three combinations of tablets we are testing. 90% felt that there was not enough evidence and 94% supported this trial. This trial fits with the number one research priority in vascular surgery from the James Lind research priority-setting exercise.

WHAT WE ARE PLANNING:

We will randomly assign 1239 participants to be prescribed one of the three tablet combinations after an angioplasty. Participants will take the tablets for up to three years. We will follow them up to see how many patients have further blockage of their leg arteries, lose their leg, have a heart attack or stroke, die or have a major bleed. We will also measure their quality of life and assess how cost-effective the tablets are to the National Health Service (NHS).

PATIENT AND PUBLIC INVOLVEMENT (PPI):

We had two members of the public on the trial development group. One takes blood-thinning tablets for blocked leg arteries and one has parents who died of blocked leg arteries. Ten people who had taken blood thinners confirmed their acceptance of being involved in a trial of blood thinners to prevent amputation. Subsequently, six people who had taken blood thinners helped develop the trial and what it would measure. For example, they had a clear preference for preventing amputation resulting from blocked arteries and their feedback reduced the number of questionnaires.

DISSEMINATION:

We will publish the trial findings in medical journals and present them at conferences. International guidelines will be updated. Participants will be informed of the trial results by a card or letter. A stakeholder meeting will be held at the end of the trial.

4 Background

4.1 Background:

CLTI is the most devastating consequence of peripheral arterial disease (PAD), leading to leg amputation and death when untreated (1). CLTI causes between 16,500-33,000 deaths and over 3500 amputations per year in the UK (2,3). Improving the blood supply of the affected limb significantly reduces these risks. The commonest way to do this is by minimally-invasive endovascular lower limb intervention ('endovascular intervention') such as angioplasty; over 6,500 are performed in the UK each year (2).

Antithrombotic (antiplatelet and/or anticoagulant) medication is given to all patients after endovascular intervention for CLTI. It improves outcomes by reducing the risk of ischaemic events such as amputation by maintaining the blood supply to the limb (4). Antithrombotic therapy also reduces the risk of secondary cardiovascular events such as myocardial infarction, stroke and related death (5). There is a historical lack of randomised controlled trial (RCT) evidence for the clinical and cost-effectiveness of the major antithrombotic regimens used in routine clinical practice in the UK. This is a major barrier to providing the best evidence-based treatment to patients.

As there is no specific Cochrane review, we performed and published a systematic review and meta-analysis (umbrella review) of RCTs for antithrombotics for PAD. Our systematic review and meta-analysis showed a stark evidence gap for antithrombotic therapy after endovascular intervention (5). We found no adequately powered RCTs but found a higher rate of major bleeding with dual antiplatelet therapy (aspirin plus clopidogrel) compared to single antiplatelet therapy for other indications in PAD. The only RCT before 2020 examining antithrombotics following endovascular intervention was a non-powered pilot trial (50 patients in each arm), which showed a signal towards a reduced amputation rate using dual antiplatelet therapy over aspirin alone (6). Another Cochrane review showed dual antiplatelet therapy prevented more ischaemic events than aspirin alone at the cost of more bleeding events in a mixed patient group including a minority with PAD (7). This review did not include as many PAD RCTs as our meta-analysis since it ostensibly examined a different patient group.

Since our systematic review, the VOYAGER PAD RCT was published in 2020. VOYAGER compared aspirin alone with aspirin plus low-dose rivaroxaban following endovascular or open intervention for PAD. VOYAGER found aspirin plus rivaroxaban significantly decreased the primary composite endpoint over aspirin alone at a cost of more major bleeding events (4). VOYAGER was sponsored by the manufacturer of rivaroxaban. Only 30% of the included patients had CLTI: the rest had less severe PAD (claudication) so were at lower risk of ischaemic events. The control arm chosen was aspirin, which was shown to be inferior to clopidogrel for treating patients with PAD 25 years ago in the CAPRIE RCT (8). Aspirin is used infrequently in clinical practice as a result (9). Rivaroxaban is expensive, on-patent (expires in 2026) and may not be cost-effective compared to dual antiplatelet therapy or clopidogrel alone, which are used more frequently in everyday clinical practice.

Observational study evidence:

Four low-quality observational studies have shown a reduction in amputation and/or death using dual antiplatelet therapy compared to aspirin alone after lower limb endovascular intervention (10–13). We conducted our retrospective study of local data using a sample size calculation, strict inclusion/exclusion criteria and clear follow-up definitions (14). We found no difference in amputation or death for the short-course (3 months) dual antiplatelet therapy compared with single therapy. Other studies used at least six months of dual antiplatelet therapy, which is known to be superior in patients who have had a myocardial infarction or undergone coronary artery stenting. The risk of major bleeding with dual antiplatelet therapy was low. The conflict between these studies and the risk/benefit balance further highlights the need for an RCT.

Questionnaire studies of UK practice and equipoise:

We published a survey of 162 UK consultants in 2019 which showed equipoise between dual antiplatelet therapy (aspirin plus clopidogrel 50%) and single antiplatelet therapy (clopidogrel or aspirin, 37%) following endovascular intervention (9). We repeated the survey in 2022 with 52 responses covering most UK vascular units. The majority of practice was clopidogrel alone (46%), dual antiplatelet therapy with aspirin plus clopidogrel (27%) and aspirin plus low-dose rivaroxaban (6%). These are also the drug choices with weak guideline recommendations (15,16) and therefore constitute our trial arms. Aspirin plus low-dose rivaroxaban will likely become more widely adopted with time after the publication of VOYAGER in 2020. To what extent this will happen is unclear as, despite a large marketing push from the company, clinical use has been limited as shown by our questionnaires. 90% of vascular surgeons still thought there was insufficient evidence to guide practice and 94% said they were willing to randomise patients in an RCT. A further survey was performed in December 2022 as part of reassuring the National Institute of Health Research (NIHR) funding panel on feasibility. Sixty-seven responses from vascular consultants in 47 UK vascular centres were received, with the same results as the previous questionnaire.

Combining the results of the literature review, questionnaire and patient and public involvement (PPI) work (outlined in subsequent sections) led to the 3-arm design and choice of antithrombotics.

Current guideline recommendations:

There is no formal National Institute for Health and Clinical Excellence (NICE) guidance in this area, only technology appraisal guidance for rivaroxaban (17) and clopidogrel (18). This is in stark contrast to cardiology (endovascular coronary intervention which is similar to endovascular lower limb intervention) where there are multiple large RCTs and detailed NICE guidance as a result (19). Other PAD guidelines can only make weak recommendations for antithrombotics after endovascular intervention due to the lack of data (15,16). Rivaroxaban 2.5mg is still on patent and is significantly more expensive than clopidogrel (rivaroxaban 2.5mg NHS tariff £1.80/day, clopidogrel £0.05/day).

4.2 Rationale for current trial/Justification of treatment options

Over 6,500 lower limb endovascular interventions are performed in the UK every year, of which 4,400 are for CLTI (2). This will rise in line with the global diabetes epidemic, as diabetes is a major risk factor for developing PAD (20,21).

CLARITY addresses six of the top ten James Lind research priorities for PAD research from the UK vascular surgery priority setting process, including the number one priority: 'What can be done to improve outcomes in CLTI?'. This is also the number one research priority from the overall exercise encompassing all vascular conditions. CLARITY also addresses 'How can we reduce progression of arterial disease?', 'Can we develop a CLTI care pathway to ensure optimal management?', 'What is

the best medical therapy for PAD?', 'How can we reduce the cardiovascular risk for PAD patients?' and 'What is the optimal antiplatelet therapy following lower limb revascularisation?'.

The trial drug combinations are all currently used in UK clinical practice (clopidogrel alone 46%, dual antiplatelet therapy with aspirin plus clopidogrel 27% and aspirin plus low-dose rivaroxaban 6%) following endovascular intervention for CLTI although there is no current NICE recommendation. The selection of drugs for the three arms was collaboratively determined with input from PPI and UK-based clinician users. The clopidogrel-alone and aspirin-plus-clopidogrel arms were co-produced by three studies in 2019, including a questionnaire with responses from 162 consultant-level vascular surgeons and interventional radiologists (9), qualitative discussions with 10 vascular surgeons and interventional radiologists, and a PPI group meeting with 8 patients. In 2022, two questionnaires with responses from UK consultant vascular surgeons and interventional radiologists reaffirmed practices, confirmed equipoise, and assessed feasibility. A second PPI group meeting involving 6 patients discussed the results of the first PPI group and the second questionnaire, confirming acceptability and leading to the addition of an aspirin-plus-rivaroxaban arm, and prompting the inclusion of a futility analysis.

CLARITY will further address (i) the first research priority from the international CLTI guideline from the European and American societies for vascular surgery: 'Define the optimal antithrombotic regimen (safety and efficacy) in patients with CLTI to reduce cardiovascular and limb specific events' (1), and (ii) the number one intervention research priority from the European Society for Vascular Surgery antithrombotic guideline, 'RCTs comparing single antiplatelet, dual antiplatelets and antiplatelet plus low dose anticoagulants post endovascular intervention. Focus on high-risk groups' (15).

The target population fits within multiple groups identified as under-served by clinical research in the INCLUDE project (22) and National Confidential Enquiry into Patient Outcome and Death 2022 healthcare inequalities review (23).

5 Trial objectives/endpoints and outcome measures

CLARITY aims to provide the definitive clinical and cost-effectiveness evidence for antithrombotic therapy following endovascular intervention for patients with CLTI so that policy makers will be able to make clear recommendations.

5.1 Primary objective

The primary objective of CLARITY is to evaluate the clinical effectiveness (using the outcomes listed in 5.3) of three antithrombotic regimens following endovascular intervention for CLTI: clopidogrel alone; aspirin plus clopidogrel; aspirin plus low-dose rivaroxaban.

5.2 Secondary objectives

The secondary objectives are to evaluate the clinical and cost-effectiveness outcomes listed in 5.4, and to evaluate the delivery of the CLARITY trial and trial interventions through the qualitative process evaluation.

5.3 Primary outcomes measures

The primary clinical effectiveness endpoint is a composite event-free survival time examined over the trial duration (36 months) comprising:

- Acute limb ischaemia
- Major lower limb amputation
- Myocardial infarction

- Ischaemic stroke
- All-cause mortality

The primary safety outcome is the International Society for Thrombosis and Haemostasis (ISTH) defined major- or clinically relevant non-major bleeding*.

*Clinically relevant non-major bleeding is bleeding that results in hospitalisation, medical or surgical intervention for bleeding, an unscheduled clinical visit, or a change in antithrombotic therapy (24).

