14.	Bleeding events	CRF/Medic al notes	ISTH defined clinically relevant minor bleeding resulting in: - Hospitalisation; - Medical or surgical intervention; - Unscheduled clinical visit/evaluation e.g. telephone/videocall by clinician; - A change in antithrombotic therapy				X	Х	X	X	X			Primary safety outcomes
15.	Bleeding events	CRF/Medic al notes	BARC and TIMI-defined major bleeding including: - Overt bleeding less than type 3 criteria that led to hospitalisation; increased level of care; nonsurgical medical intervention; unscheduled clinical evaluation e.g. telephone/videocall by clinician				х	Х	Х	X	X			Secondary Outcomes

Asse	essment	Source Data	Data type/Measure	Screening	Baseline assessment	Randomisation	Clinical Assessment: 2 months	6 month Follow-up	12 month Follow-up	24 month Follow-up	36 month Follow-up	АБ НОС	Responsible for Data Collection	Justification
			- Required surgical intervention or intravenous vasoactive agents - Cardiac tamponade - Hemoglobin drop related to bleed - Hemoglobin drop amount 3 g/dL and more - Symptomatic bleeding in a critical area - Leading to any transfusion - Probable fatal bleeding - Definite fatal bleeding											
16.	Bleeding events	CRF/Medic al notes	Minor bleeding: Not meeting major bleeding criteria				Х	Х	Х	Х	Х			Secondary Outcomes
17.	Post- Operative	CRF/Medic al notes	Protocol-specified MALE and MACE events including: - Major or minor amputation (trial limb) - Reintervention (trial limb) - Venous thromboembolism - Major amputation (contralateral limb) - Acute coronary syndrome - Ischaemic stroke				х	Х	X	Х	Х			Secondary Outcomes

Asso	essment	Source Data	Data type/Measure	Screening	Baseline assessment	Randomisation	Clinical Assessment: 2 months	6 month Follow-up	12 month Follow-up	24 month Follow-up	36 month Follow-up	AD HOC	Responsible for Data Collection	Justification
			- Recurrent CLTI											
18.	Healing of tissue loss		Healing tissue loss defined as full epithelialisation (yes/no)				X	Х	Х	Х	Х			Secondary Outcomes
19.	Patency following revascularisa tion	CRF/Medic al Notes	- Primary patency of artery (yes/no) - Secondary patency of artery (yes/no)				Х	Х	X	Х	Х			Secondary Outcomes
20.	Reinterventi on rates	CRF/Medic al notes					Х	Х	Х	Х	Х			Secondary Outcomes
21.	Resource Use	Questionn aire / CRF	Client Service Receipt Inventory (CSRI)					Х	Х	Х	Х	Х	Participant reported / Site Research team	Secondary outcome
22.	Qualitative Interviews	Audio recordings										Х		Qualitative/SWAT

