12.2.1 Month 2 – Clinical follow-up

Within two months of the revascularisation, data from the routine clinical follow-up appointment, attended by the patients and conducted by their clinicians, will be collected by research staff. Current medications, all primary composite and bleeding outcomes, and all secondary and tertiary outcomes other than health economic data will be assessed, including:

Primary composite and bleeding outcomes

- 1. A composite event-free survival time of:
 - i. acute limb ischaemia
 - ii. major lower limb amputation
 - iii. myocardial infarction
 - iv. ischaemic stroke
 - v. all-cause mortality
- 2. Major bleeding

Secondary outcomes

- 1. Major adverse limb events (MALE) defined as amputation or any major reintervention;
- 2. Major adverse cardiovascular events (MACE) defined as recurrent CLTI, amputation affecting the contralateral limb, acute coronary syndrome or stroke;
- 3. BARC and TIMI major bleeding;
- 4. Minor bleeding;
- 5. Primary and secondary patency of artery;
- 6. Reintervention rates;
- 7. Healing of tissue loss;
- 8. Participant-reported health-related QoL (VascuQoL-6 and EQ-5D-5L);

- Current medications (including changes to trial drugs and reasons)
- Tertiary outcomes
- MALE using other major definitions
- 2. MACE using other major definitions
- 3. Complications from trial medications

12.2.2 Month 6 and Month 12 (and Months 24 and 36 if applicable) – follow-up

All outcomes measured at 2 months will be assessed at the 6- and 12-months follow-up time points for all participants, and also at 24 and 36 months for those recruited earlier.

A healthcare resource use CRF/Questionnaire (adapted CSRI) will additionally collect:

- Hospital admissions, emergency department attendance and outpatient attendance via medical notes.
- Community-based resource use via patient-reported questionnaire supported by a patient diary as an *aide mémoire*.

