- Remaining intercurrent events: Death is incorporated into the clinical effectiveness primary outcome. Treatment discontinuation is covered by the previous attribute.
- Population-level summary: Hazard ratios, including fixed effects for allocation and random
 effects to model heterogeneity between sites. Regression analysis results will be presented as
 point estimates with confidence intervals and p-values from a log-rank test, and Kaplan-Meier
 curves of cumulative event rates at 36 months (31,32) will be generated to compare arms over
 time.

The primary safety outcome analysis will also use a two-level Cox regression as described above but include only those participants who received at least one dose of their allocated medication ('ontreatment' population). This analysis will include safety events that occurred after receiving the first dose of the trial medication and within 5 days after receiving the last dose.

Secondary outcomes will also be analysed based on ITT (for effectiveness outcomes) or 'on- treatment' populations (for safety outcomes) and using appropriate two-level regression models depending on the type of outcome: Cox regression for time-to-event outcomes, linear regression for continuous outcomes such as QoL measures (allowing for repeated measures where appropriate), and logistic regression for binary outcomes such as reintervention rates.

Table 7. Planned outcome analysis

Outcome	Measure	Analysis	Time frame	
Composite primary	Acute limb ischaemia	Two-level Cox regression		
outcome - Composite event-	Major lower limb amputation	Two-level Cox regression	2m, 6m, 12m,	
free survival time of the following:	Myocardial infarction	Two-level Cox regression	24m and 36m	
the following:	Ischaemic stroke	Two-level Cox regression		

Outcome	Measure	Analysis	Time frame		
	All-cause mortality	Two-level Cox regression			
Primary safety outcome	Major bleeding (ISTH definition)	Two-level Cox regression	2m, 6m, 12m, 24m and 36m		
	MALE (defined as amputation or any major reintervention)	Two-level Cox regression	2m, 6m, 12m, 24m and 36m		
	MACE (defined as recurrent CLTI, amputation affecting contralateral limb, acute coronary syndrome, ischaemic stroke)	Two-level Cox regression			
Caracilar	Major bleeding (BARC definition)	Two-level Cox regression			
Secondary outcomes	Major bleeding (TIMI definition)	Two-level Cox regression			
	Minor bleeding	Two-level Cox regression			
	Primary patency of artery	Two-level logistic regression			

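### The primary safety outcome is ISTH major or clinically relevant non-major bleeding in section 5.3 and Table 2, but major bleeding only in Table 7 and the 12.2.1 visit list

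*Protocol*

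**What the plan says.** The protocol describes the primary safety outcome in several places.

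- **Section 5.3** defines it: "The primary safety outcome is the International Society for Thrombosis and Haemostasis (ISTH) defined major- or clinically relevant non-major bleeding". The footnote explains the wider part: "Clinically relevant non-major bleeding is bleeding that results in hospitalisation, medical or surgical intervention for bleeding, an unscheduled clinical visit", and adds a change in antithrombotic treatment as a further trigger.
- **Table 2** (in 12.1.1) lists ISTH major bleeding in row 13. Row 14 begins "ISTH defined clinically relevant minor bleeding resulting in" and gives essentially the same triggers as the 5.3 footnote. Both rows are justified as primary safety outcomes, at every follow-up from 2 to 36 months.
- **Section 15.1** describes the model: "The primary safety outcome analysis will also use a two-level Cox regression as described above". It restricts the analysis to participants who took at least one dose and to a window ending 5 days after the last dose. It does not say which bleeds count.
- **Table 7** fills that gap with "Major bleeding (ISTH definition"). No row covers clinically relevant non-major bleeding or the combined outcome.
- **Section 12.2.1**, under the primary composite and bleeding outcomes, has only "2. Major bleeding". Section 12.2.2 carries this forward: "All outcomes measured at 2 months will be assessed at the 6- and 12-months follow-up time points for all participants", and likewise to 24 and 36 months for early recruits.
- **Sections 13 and 13.2** name only major bleeding when listing the primary outcomes recorded on the outcomes CRF.

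A secondary outcome, minor bleeding, is described in Table 2 row 16 as: "Minor bleeding: Not meeting major bleeding criteria".

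**The concern.** A primary outcome needs one definition, and here the defining section and the analysis table disagree. This is not detail left to the statistical analysis plan. The protocol fixes the event twice, so an analysis plan that follows 5.3 departs from Table 7, and one that follows Table 7 departs from 5.3.

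The choice matters for three reasons. First, the stated aim is to weigh ischaemic benefit against bleeding, and this outcome carries the bleeding side. Second, patients and clinicians know the allocation, and whether a bleed leads to an unscheduled visit or a change of therapy can be influenced by that knowledge. The narrower ISTH criteria (death, critical site, haemoglobin fall, transfusion) leave less room for this. Third, 15.1.1 plans an interim analysis of the co-primary outcomes. If bleeding is one of them, its definition is needed by then.

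**Working it through.** There is no figure for the safety outcome to reproduce: the protocol gives no bleeding rate, margin or power for it. The sample size in 14.3 rests on the effectiveness outcome (157 + 115 + 115 = 387 events), so neither bleeding definition affects it.

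**Step 1: do the places differ in substance?** Take three hypothetical bleeds and classify each using the protocol's own criteria.

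| Bleed | 5.3 and Table 2 rows 13-14 | Table 7 and 12.2.1 (major read as ISTH major) |
|---|---|---|
| A. Haemoglobin fall of 2 g/dL or more | Primary safety event | Primary safety event |
| B. Overt bleed leading to admission; no critical site, haemoglobin fall below 2 g/dL, no transfusion | Primary safety event | Not a primary safety event |
| C. Bleed whose only consequence is a change of antithrombotic drug at a planned visit | Primary safety event | Not a primary safety event |

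B and C change status, so the two descriptions are different endpoints. Sections 13 and 13.2 create a related problem. They take the named primary outcomes off the SAE form and put them on the outcomes CRF, but name only major bleeding. Bleed B is a primary safety event under 5.3 and is not named there.

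**Step 2: which way does the difference run?** The combined outcome contains every major bleed. Let d be the number of participants with an event in a pairwise comparison; then d(combined) is at least d(major). With equal arms, SE(ln HR) is about 2/√d. The confidence interval on the log scale for the combined outcome is therefore √[d(major)/d(combined)] times as wide as that for major bleeding. The hazard ratio itself may also differ, because non-major bleeds need not respond to treatment as major ones do. Without rates, neither effect can be given a number.

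**Step 3: does row 16 overlap the primary safety outcome?** Row 16 does not say which major criteria it means.

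- If ISTH major, bleeds B and C both count as secondary minor bleeds and, under 5.3, as primary safety events.
- If the BARC/TIMI list in row 15, bleed B is already under a major heading, since that row includes overt bleeding leading to admission, non-surgical medical treatment or unscheduled evaluation. Only bleed C is then minor, because a change of antithrombotic therapy is the one 5.3 trigger with no counterpart in row 15.

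The extent of overlap depends on the reading, and the protocol does not choose.

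The synopsis list of primary outcomes is incomplete in the text available for this review and is not relied on.

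**The case against.** The best defence is that Table 7 and 12.2.1 use short labels. Section 5.3 is the defining section and is clear, and 15.1 refers back to the primary safety outcome without redefining it. Table 7 abbreviates elsewhere: MALE loses its restriction to the trial limb and BARC loses its grades. Section 12.2.1 drops the ischaemic qualifier from stroke. This may well be how the difference arose. It does not remove it, because Table 2 treats ISTH major and clinically relevant bleeding as separate categories, and Table 7 names the first with its ISTH qualifier.

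Four stronger readings are tempting, and the document does not support them.

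- **That clinically relevant non-major bleeds are not scheduled for collection.** Table 2 row 14 schedules them at every follow-up. The omission is in the narrative visit list, not in the schedule of assessments.
- **That every such bleed is counted twice, as primary and as minor.** Row 16 is ambiguous, and on one reading most of them are not minor. Overlap between bleeding scales is also not an error in itself.
- **That the endpoint could be picked after the data are seen.** Section 15.1 requires the analysis plan to be agreed and signed off before any analysis, and 14.2 has the statistician perform the primary analysis blind to allocation.
- **That the two event counts differ several-fold.** Any such figure needs assumed bleeding and death rates, and must allow for the on-treatment window, which shortens exposure.

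**Conclusion.** The inconsistency stands. Section 5.3 and Table 2 rows 13-14 define one primary safety outcome; Table 7 and 12.2.1, with 12.2.2, give a narrower one, and sections 13 and 13.2 follow the narrower wording. Followed as written, Table 7 would have the primary safety model analyse a different endpoint from the one the protocol defines. This conclusion rests on the text alone and needs no assumed rates. Its numerical effect on the hazard ratio and its precision cannot be derived from the protocol. The effectiveness analysis and sample size are unaffected, and no data item is missing. The ambiguity in row 16 is a smaller, related point.

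**What to change.** 1. In Table 7 and 12.2.1, give the primary safety outcome as ISTH major or clinically relevant non-major bleeding, matching 5.3 and Table 2. This is the smaller change, because the defining section and the data schedule already agree.
2. Reconcile sections 13 and 13.2 with that definition, so that it is clear on which form a clinically relevant non-major bleed that also meets a seriousness criterion is recorded.
3. In Table 2 row 16, state which major criteria are meant, and word it so that secondary minor bleeding excludes clinically relevant non-major bleeds already counted in the primary safety outcome. Use one term in row 14 and 5.3, which now say minor and non-major for the same category.
4. Optionally, report ISTH major bleeding alone as a supportive analysis.

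The cost is a wording amendment, best made before the analysis plan is signed off. It needs no new data items, visits or participants.
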